#### 6.2.1. Inclusion Criteria

A patient must meet the following criteria to be eligible for inclusion in the study:

1. Male or female  $\geq 6$  to  $< 12$  years of age at time of screening visit
2. Diagnosis of AD according to the American Academy of Dermatology consensus criteria ([Eichenfield 2003](#)) at screening visit
3. Chronic AD diagnosed at least 1 year prior to the screening visit
4. IGA = 4 at screening and baseline visits
5. EASI  $\geq 21$  at the screening and baseline visits
6. BSA  $\geq 15\%$  at screening and baseline visits
7. Baseline worst itch score weekly average score for maximum itch intensity  $\geq 4$

NOTE: Baseline worst itch average score for maximum itch intensity will be determined based on the average of daily worst itch scores for maximum itch intensity (the daily score ranges from 0 to 10) during the 7 days immediately preceding randomization. A minimum of 4 daily scores out of the 7 days is required to calculate the baseline average score. A complete daily score consists of answers to both questions.

- “What was the worst itch you had today?”
- “What was the worst itch you had last night?”

For patients who do not have at least 4 daily scores reported during the 7 days immediately preceding the planned randomization date, randomization should be postponed until this requirement is met, but without exceeding the 77-day maximum duration for screening plus TCS standardization.

8. With documented recent history (within 6 months before the baseline visit) of inadequate response to topical AD medication(s). For more information, see the note below.

NOTE:

- Inadequate response is defined as failure to achieve and maintain remission or a low disease activity state (comparable to IGA 0=clear to 2=mild) despite treatment with a daily regimen of TCS of medium to high potency ( $\pm$ TCI as appropriate), applied for at least 28 days
  - Patients with documented systemic treatment for AD in the past 6 months are also considered as inadequate responders to topical treatments and are potentially eligible for treatment with dupilumab after appropriate washout.

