### 8.2.2.1. Patient Assessment of Pruritus Using Worst Itch Scale

The worst itch scale is a simple assessment tool that patients will use to report the intensity of their pruritus (itch). This is an 11-point scale (0 to 10) in which 0 indicates no itching while 10 indicates worst itching possible. Patients will be asked the following 2 questions:

“What was the worst itch you had today?”

“What was the worst itch you had last night?”

Patients will be asked to provide answers to these 2 questions daily throughout the entire study (screening period, treatment period, and follow-up period; see time point in Section 8.1). Both questions will be answered in the evening (it is recommended that the questions be answered and the responses provided in the diary in the 6:00 PM to 11:00 PM local time window). The daily worst itch score will be calculated as the worse of the scores for the 2 questions.

Patients will be instructed on using the patient diary to record their worst itch score at the screening and baseline visits. Clinical sites will check and remind patients to complete the diary at each visit.

This questionnaire measures concept(s), which are known only/best to the patient suffering from AD. As such the questionnaire is designed for self-report. Where possible the patient should read and complete the questionnaire alone. Where required, a caregiver (parent or other) can read the questions and response options aloud to the person with AD. However, it is important that the patient’s selected responses to the questions are entered directly into the questionnaire. The caregiver must not influence or question the response given by the person with AD. This should be communicated to caregivers during the first visit. A field to indicate whether the question and response options were read out to the patient by caregiver has been added to the first page of the diary/questionnaire.

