### 10.5.2.2. Secondary Efficacy Analysis

For binary endpoints, the secondary efficacy analysis will use the same approach as that used for the primary analysis.

For continuous endpoints:

- The multiple imputation (MI) with analysis of covariance (ANCOVA) model will be used as the primary analysis method. Patients' efficacy data through week 16 after the rescue treatment use will be set to missing first, and then be imputed by the multiple imputation method. Missing data from the FAS will be imputed 40 times to generate 40 complete datasets by using the SAS procedure MI following the 2 steps below:
  - Step 1: The monotone missing pattern is induced by Markov Chain Monte Carlo (MCMC) method in MI procedure using seed number 12345.
  - Step 2: The missing data at subsequent visits will be imputed using the regression method for the monotone pattern with seed number 54321 and adjustment for covariates including treatment groups, randomization strata (baseline weight group and region), and relevant baseline.
- The week 16 data of each of the 40 complete datasets will be analyzed using an analysis of covariance (ANCOVA) model with treatment, randomization strata (baseline weight group and region), and relevant baseline included in the model, and the SAS MIANALYZE procedure will be used to generate valid statistical inferences by combining results from the 40 analyses using Rubin's formula.
- If a patient receives rescue treatment, the efficacy data collected after rescue treatment is initiated will be treated as missing. All efficacy data will be used for analysis regardless of whether the patient is on study treatment or discontinues the study treatment but remains in the study.
- In addition to the MI method described above, sensitivity analyses such as ANCOVA model with LOCF, MI method with ANCOVA model on all observed data regardless of rescue use will be conducted. Additional details on sensitivity analyses will be provided in the SAP.

Time to event endpoint will be analyzed using the Cox proportional hazards model. Kaplan-Meier curves will also be provided.

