5.7. Analyses of Efficacy Variables

For all efficacy variables, the analysis will be comparisons of each dupilumab regimen and the placebo treatment groups. The following null and alternative hypotheses for the primary endpoint will be tested for each dupilumab regimen group and the placebo group:

H0: $p_{dupilumab} = p_{placebo}$, where p stands for the percent of responders in a treatment group

H1: $p_{dupilumab} \neq p_{placebo}$.

The analyses of efficacy variables are described in the subsections below and summarized in [Appendix 10.1](#).

Subgroups are defined by key baseline factors recorded on the CRF and listed to be considered for primary and key secondary efficacy analyses:

- Age group (≥ 6 to < 9 , ≥ 9 to < 12)
- Sex (Male, Female)
- Ethnicity: Hispanic or Latino (no/yes)
- Race (White, Black or African American, Asian, Other)
- Duration of AD (< 5 years, ≥ 5 years)
- Age of disease onset (< 2 years, ≥ 2 years)

- Age of disease onset (<5 years, ≥5 years)
- Family history of atopic disease (Yes/No)
- Baseline weight group (<30 kg, ≥30 kg)
- BMI (<20, ≥20)
- Region (North America, Europe)
- Baseline severe EASI (<25, ≥25)
- Baseline moderate-to-severe EASI (<20, ≥20)
- Baseline worst itch scale (<7, ≥7)
- Body Surface Area (BSA) (≥10%-<30%, ≥30%-<50%, ≥50%)
- Baseline SCORAD score (<50, ≥50)
- Previous usage of ciclosporin (CsA) (Yes, No)
- Previous usage of methotrexate (MTX) (Yes, No)
- Previous usage of Azathioprine (Aza) (Yes, No)
- Previous use of systemic immunosuppressants for AD (Yes, No)
- History of asthma (Yes, No)
- History of nasal polys (Yes, No)
- History of allergic rhinitis (Yes, No)
- History of food allergies (Yes, No)

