5.7.2. Analyses of Secondary Efficacy Variables

All secondary endpoints will be evaluated on the FAS. Selected secondary endpoints will be evaluated in the mFAS as sensitivity analyses.

The binary secondary efficacy endpoints will be analyzed using the same approaches used for the analysis of the primary endpoints.

The continuous endpoints will be analyzed using analysis of covariance (ANCOVA) model as the primary analysis method with multiple imputation (MI) method for missing data. Patients' efficacy data through week 16 after the rescue treatment use will be set to missing first, and then be imputed by MI method. To account for the uncertainty in the imputation, missing data from the FAS will be imputed 40 times to generate 40 complete data sets by using the SAS procedure MI following the 2 steps below:

Step 1: The monotone missing pattern is induced by Markov Chain Monte Carlo (MCMC) method in MI procedure using seed number 12345. The monotone missing pattern means that if a patient has missing value for a variable at a visit, then the values at all subsequent visits for the same variable are all missing for the patient.

Step 2: The missing data at subsequent visits will be imputed using the regression method for the monotone pattern with seed number 54321 and adjustment for covariates including treatment groups, randomization strata (baseline weight group and region), and relevant baseline.

Once imputations are made, the week 16 data of each of the 40 complete datasets will be analyzed using ANCOVA model with treatment, randomization strata (baseline weight group and region), and relevant baseline included in the model, and the SAS MIANALYZE procedure will be used to generate valid statistical inferences by combining results from the 40 analyses using Rubin's formula.

The imputation model will include:

- The covariates included in the ANCOVA model, including the treatment group, the baseline value and the randomization strata (baseline weight group and region)
- Measured endpoint values at every clinic visit (i.e. week 1, 2, 3, 4, 8, 12 and week 16)

Categorical variables included in above model (i.e., treatment group and randomization strata) are not expected to be missing.

To account for the impact of rescue treatment on the efficacy effect:

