- Continuous efficacy endpoints: if a patient receives rescue treatment that specifies the patient as a non-responder according to the above rules for binary efficacy endpoints, the data collected after rescue treatment is initiated will be treated as missing.

Sensitivity analyses

In addition to the MI method described previously, sensitivity analyses for the continuous endpoints for EASI and/or Pruritus worst itch scale will be conducted as described below.

1. The sensitivity analysis based on all observed data regardless if rescue treatment is used or data is collected after withdrawal from study treatment using MI method will be performed.
2. This sensitivity analysis will use ANCOVA model, including the treatment group, the baseline value and the randomization strata. The efficacy data will be set to missing after rescue treatment is used. The post-baseline LOCF method will then be used to impute missing values.
3. This sensitivity analysis will use ANCOVA model, including the treatment group, the baseline value and the randomization strata. The efficacy data will be set to missing after rescue treatment is used. The post-baseline worst observation carried forward (WOCF) method will then be used to impute missing values.

Time to onset of effect on pruritus as measured by proportion of patients with improvement (reduction) of weekly average of daily Pruritus worst itch scale ≥ 4 and ≥ 3 from baseline during the 16-week treatment period will be calculated for each patient as the date of having the first event - the first study drug dose date + 1 day. Patients not having either event during the treatment period will have their time censored at the end of treatment period. These times to onset of effect on pruritus will be analyzed using the Cox proportional hazards model including treatment and randomization strata as factors, The hazards ratio, its 95% confidence interval and p-value will be reported. Kaplan-Meier curves will be provided.

The mean weekly dose of TCS use during the treatment period endpoints will be analyzed using an ANCOVA model with treatment, randomization strata (baseline weight group and region) and relevant baseline included in the model.

Analysis of incidence of TEAE-related variables

- Incidence of skin infection TEAE (excluding herpetic infections) from baseline through week 16
- Incidence of treatment-emergent serious adverse events from baseline through week 16

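### The Cox model for time to itch response leaves out baseline worst itch, forgoing modest power and protection against imbalance on two secondary endpoints

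*SAP*

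**What the plan says.** Protocol 4.2.2 and SAP 4.4.2 list two time-to-onset endpoints among the other secondary endpoints: time to a reduction of at least 4 points, and of at least 3 points, in weekly-average worst itch over 16 weeks.

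- **Cox model.** Protocol 10.5.2.2 names no covariates: "Time to event endpoint will be analyzed using the Cox proportional hazards model". SAP 5.7.2 fills this in: the times will be "analyzed using the Cox proportional hazards model including treatment and randomization strata as factors". The strata are weight group and region. The hazard ratio, its 95% interval and a p-value will be reported. The itch row of SAP Appendix 10.1 says only that a Cox model is used.
- **Continuous endpoints.** The same SAP section uses an "ANCOVA model with treatment, randomization strata (baseline weight group and region), and relevant baseline included in the model". The analysis of weekly topical steroid dose also includes the relevant baseline.
- **Responder endpoints at the same thresholds.** "The binary secondary efficacy endpoints will be analyzed using the same approaches used for the analysis of the primary endpoints", that is, a CMH test by randomization strata without baseline itch.
- **Baseline itch.** Inclusion criterion 7 (Protocol 6.2.1) requires a "Baseline worst itch score weekly average score for maximum itch intensity" of at least 4, from at least 4 of the 7 days before randomization. The scale runs from 0 to 10 (Protocol 8.2.2.1). SAP 5.7 lists baseline itch, cut at 7, as a subgroup factor.

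**The concern.** The event is an absolute fall from baseline on a bounded scale, so the starting value is part of its definition. Two children with the same proportional improvement can differ in whether and when they reach a 4-point fall, purely because they started at different levels. Weight group and region are in the model because they were stratification factors. Nothing in the model reflects baseline itch, and randomization was not stratified on it.

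Two things are at stake. Leaving a prognostic covariate out of a Cox model gives a marginal hazard ratio that lies closer to 1 than the conditional one, with a smaller test statistic. And a chance difference between arms in baseline itch passes into the estimate without correction.

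**Working it through.** **Plan's own figure.** There is none to reproduce. The powers in Protocol 10.2 and SAP 2.2 concern IGA 0 or 1 and EASI-75 only.

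**How baseline enters the event.** Required proportional fall = threshold ÷ baseline.

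| Baseline | 4-point fall | 3-point fall |
|---|---|---|
| 4 | 4/4 = 100% | 3/4 = 75% |
| 7 | 4/7 = 57% | 3/7 = 43% |
| 10 | 4/10 = 40% | 3/10 = 30% |

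**Inputs from the documents.** 110 per arm (Protocol 10.2), 2-sided 0.05, 16 weeks, patients without an event censored at the end of treatment, entry at 4 or more on a 0 to 10 scale.

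**Assumed inputs.** Baseline distribution, event rates, treatment effect and prognostic strength of baseline. Dropout was not modelled in the simulations tabulated below.

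**Measure.** Z = log HR ÷ SE. The squared-Z ratio is (Z with baseline ÷ Z without)². Because squared Z grows roughly in proportion to events, a ratio of 1.05 is worth about 5% more events.

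**Simulations 1 and 2.** 400 trials per row, weekly event times, Efron ties, treatment plus two binary strata, with and without baseline. Baseline is normal, mean 7.5, SD 1.5, truncated to 4–10. Simulation 1 assumes proportional hazards with a set effect of baseline. Simulation 2 generates itch trajectories with mean improvement of 25% on placebo against 40% or 50% on active, SD 30 points.

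| Scenario | HR without → with | SE(log HR) without → with | Power without → with | Squared-Z ratio |
|---|---|---|---|---|
| 1: baseline HR per point 1.00 | 1.60 → 1.60 | 0.204 → 0.205 | 62% → 61% | 0.99 |
| 1: 1.23 | 1.61 → 1.63 | 0.205 → 0.206 | 64% → 66% | 1.04 |
| 1: 1.49 | 1.62 → 1.68 | 0.204 → 0.205 | 67% → 72% | 1.15 |
| 1: 1.84 | 1.50 → 1.60 | 0.202 → 0.203 | 52% → 64% | 1.33 |
| 2: 4-point, 25% v 40% | 1.88 → 1.91 | 0.230 → 0.231 | 79% → 79% | 1.04 |
| 2: 3-point, 25% v 40% | 1.72 → 1.75 | 0.184 → 0.185 | 85% → 87% | 1.05 |
| 2: 4-point, 25% v 50% | 2.72 → 2.82 | 0.221 → 0.222 | 99.8% → 99.8% | 1.06 |

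The last column follows from the rounded means in each row. For the first trajectory row: (ln 1.91/0.231)² ÷ (ln 1.88/0.230)² = (0.6471/0.231)² ÷ (0.6313/0.230)² = 7.85 ÷ 7.53 = 1.04. The Monte Carlo error of each power is at most √(0.25/400) = 2.5 points.

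In the trajectory rows the fitted baseline hazard ratio was 1.31, 1.19 and 1.30 per point, well below the 1.84 that gave the large gain.

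**Simulation 3.** Itch trajectories with SD 35 points, 25% v 40%, 300 trials per scenario, varying the baseline distribution.

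| Baseline | Squared-Z ratio, 4-point | Squared-Z ratio, 3-point | Power change |
|---|---|---|---|
| Uniform 4–10 | 1.13 | 1.10 | 64% → 67%; 71% → 73% |
| Truncated N(7.5, 1.5) | 1.05 | 1.06 | +3 points each |
| Truncated N(8, 1.2) | 1.04 | 1.02 | +2; 0 points |

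With uniform baselines the hazard ratio moved from 1.77 to 1.84 (4-point) and from 1.68 to 1.73 (3-point). A separate run of 400 trials per scenario, with effects of 40% or 50%, gave ratios of 1.11 and 1.12, 1.05 and 1.06, and 1.03 and 1.04 for the same three distributions.

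**Chance imbalance (simulation 3).** In five of six scenarios the log hazard ratio without baseline correlated 0.18 to 0.32 with the arm difference in mean baseline itch. With baseline in the model this fell to 0.01–0.08. The sixth scenario showed no such pattern (0.01 → −0.11).

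**The case against.** The strongest case is that nothing here is wrong. Randomization makes the strata-adjusted comparison valid, and its error rate already allows for chance imbalance. The SAP is also consistent within event-type analyses: the itch responder endpoints at the same thresholds use CMH without baseline, and the safety Cox models in SAP 5.8.1 use treatment and strata only. Neither time-to-onset endpoint is among the 22 steps of the hierarchy in SAP 5.7.2. Baseline itch will be tabulated by arm, so an imbalance would be visible. The gain rests wholly on assumed inputs, and simulating proportional improvement makes baseline prognostic by construction. All of this stands. It sets the priority, but it does not give a reason to leave the covariate out.

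Three stronger readings are tempting, and the documents do not support them.

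- **A reader might infer that baseline decides whether the event is possible at all.** Criterion 7 puts every eligible child at 4 or above, so both falls can be reached. Baseline governs difficulty. Exceptions would be children randomized below 4 in breach of the criterion, or before Amendment 1 added it; the documents give no number for either.
- **A reader might infer that precision is lost.** The standard error rose by about 0.001 in every row of the first table. The gain comes from a conditional hazard ratio further from 1. That is a change of estimand, so the difference should not be called bias.
- **A reader might want baseline itch as an extra CMH stratum for the responder endpoints.** Cutting at 7 would double the strata from 4 to 8 and depart from Protocol 10.5.2.2, which gives binary secondary endpoints the primary approach.

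**Conclusion.** The point holds as a low-priority efficiency improvement. SAP 5.7.2 omits a covariate that is already collected and that is part of the event definition.

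Under the assumed itch trajectories the cost is about 2% to 13% in squared Z. The top of that range needs baselines spread evenly over 4 to 10; the two more concentrated distributions give 2% to 6%. Power changes by about 0 to 5 points in the trajectory runs and for a baseline hazard ratio up to about 1.5 per point. It reaches 12 points only at 1.84 per point, and there is no gain if baseline is not prognostic. Protection against chance imbalance is a further, smaller benefit. No confirmatory conclusion depends on the choice, because neither endpoint is under alpha control.

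**What to change.** In SAP 5.7.2, and in the itch row of Appendix 10.1, specify a Cox model with treatment, randomization strata and baseline weekly-average worst itch as a continuous covariate. State that the reported hazard ratio is conditional on baseline itch. Leave the CMH analyses of the responder endpoints unchanged.

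The cost is one sentence and one covariate, with no new data. The downside is that the hazard ratio is no longer marginal over baseline, so it is not directly comparable with one adjusted for strata only. If that matters, the baseline-adjusted model can be a named supportive analysis.

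Timing matters. SAP section 1 allows revisions based on blinded review before final lock. However, the optional first-step analysis (SAP section 7) would be the final analysis of the secondary endpoints, so the change must precede that unblinding. If treatment codes have already been opened, report the adjusted model as post hoc.

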5.7.3. Subgroup Analysis

Subgroup for the primary endpoint and key secondary efficacy will be analyzed based on FAS. The analysis method for the subgroup will be the same as the primary analysis described in Section 5.7.1 and Section 5.7.2. Interactions between the subgroups and treatment groups will also be tested using the logistic regression model for the categorical endpoints, and using the ANCOVA model for the continuous endpoints. The model will include randomization strata, treatment group, subgroup, treatment by randomization strata interaction and treatment by subgroup interaction as factors. P-values for the interaction term will be reported. We will consider interaction effect as significant if P-value is greater than 0.1.

Forest plots of the primary and key secondary efficacy endpoints across subgroups will be generated.

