4.4.2. Secondary Efficacy Variables

The key secondary endpoints are:

- Proportion of patients with EASI-75 ($\geq 75\%$ improvement from baseline) at week 16 (this is not a secondary endpoint for ex-US countries as it is already a co-primary endpoint)
- Percent change in EASI score from baseline to week 16
- Percent change from baseline to week 16 in weekly average of daily worst itch score

Worst itch scale

The worst itch scale is a simple assessment tool that patients will use to report the intensity of their pruritus (itch). This tool is composed of two questions and each question is an 11-point scale (0 to 10) in which 0 indicates no itching while 10 indicates worst itching possible. Patients will be asked the following 2 questions:

- “What was the worst itch you had today?”
- “What was the worst itch you had last night?”

Patients will be asked to provide answers to these 2 questions daily throughout the entire study (screening period, treatment period, and follow-up period; see time point in [Appendix 10.2](#)). The daily worst itch score will be calculated as the worse of the scores for the 2 questions on a given day. Any day with one score only should be discarded as a “missing score day”.

Patients will be instructed on using the patient diary to record their worst itch score at the screening and baseline visits. Clinical sites will check and remind patients to complete the diary at each visit.

The baseline worst itch scale score is defined as the prorated average of the worst itch scale scores reported continuously for 7 days right before the baseline visit (i.e. study day -7 to day -1). A minimum of 4 daily scores out of the 7 days is required to calculate the baseline average score. For post-baseline worst itch scale score, the weekly mean of daily worst itch score is calculated as the prorated average of the reported daily worst itch score within the week. For example, if there are 3 scores in a week, the prorated average = $(\text{score1} + \text{score2} + \text{score3})/3$.

Other secondary endpoints are:

- Change from baseline to week 16 in weekly average of daily worst itch score
- Proportion of patients with EASI-50 at week 16
- Proportion of patients with EASI-90 at week 16
- Change from baseline to week 16 in percent BSA affected by AD
- Percent change from baseline to week 16 in SCORAD
- Proportion of patients with improvement (reduction) of weekly average of daily worst itch score ≥ 4 from baseline at week 16

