5.12. Analysis of Biomarker Data

Descriptive statistics for the observed values, change from baseline and percent change from baseline values by treatment and visit will be provided for the following biomarker variables:

- TARC
- total serum IgE
- Serum Immunoglobulin profile (IgG/IgM/IgA, IgG subclasses)
- Lactate dehydrogenase (LDH)

The Wilcoxon signed-rank test will be used to test if the change or percentage change from baseline value is significantly different from zero. P-value will be reported.

Exploratory analyses for the difference between dupilumab groups and placebo on the change from baseline and percent change from baseline values will be performed using a rank-based ANCOVA model with treatment group as a fixed effect, and the relevant baseline values as covariate. Missing value will be imputed by LOCF method for visits between post-baseline to week 16. After week 16, no imputation will be made. P-value for difference from placebo will be provided.

Correlation of baseline TARC (measured value) and IgE (measured value) with the following clinical endpoints will be explored using ANCOVA model. The model includes the below clinical endpoint as the dependent variable and the log₁₀ based transformed baseline biomarker data, treatment group and their interaction as the predictor variables. Model coefficients and P-value will be provided to indicate significance of the correlation/association.

- Percent change from baseline to week 16 in EASI score
- Percent change from baseline to week 16 in weekly average of worst itch scale
- Change from baseline to week 16 in percent BSA
- Percent change from baseline to week 16 in SCORAD

Correlation of baseline TARC (measured value) and IgE (measured value) with the following clinical endpoints will be explored using the logistic model. The model includes the responder/nonresponder of below clinical endpoint as the dependent variable and the log₁₀ based transformed baseline biomarker data, treatment group and their interaction as the predictor variables. Model coefficients and P-value will be provided to indicate significance of the correlation/association.

- IGA 0-1 at week 16
- EASI-75 at week 16
- improvement (reduction) of weekly average of worst itch scale ≥ 4 from baseline to week 16

Association of positivity to at least one antigen-specific IgE with the following clinical endpoints will be explored using CMH test stratified by weight. The risk ratio and p-value will be provided.

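### SAP 5.7.3 does not name the baseline value in the interaction model for the continuous key endpoints, although the 5.7.2 ANCOVA for the same endpoints includes it; read literally, the interaction test gives up some precision.

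*SAP*

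**What the plan says.** SAP 5.7.3 makes two statements about subgroups. For the subgroup analyses themselves, "The analysis method for the subgroup will be the same as the primary analysis described in Section 5.7.1 and Section 5.7.2". For the interaction tests, it specifies logistic regression for categorical endpoints and "using the ANCOVA model for the continuous endpoints". One list of terms then serves both model types: "The model will include randomization strata, treatment group, subgroup, treatment by randomization strata interaction and treatment by subgroup interaction as factors". The interaction p-values are to be reported, and forest plots are planned for the primary and key secondary endpoints.

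In SAP 5.7.2, each imputed dataset for a continuous endpoint is "analyzed using ANCOVA model with treatment, randomization strata (baseline weight group and region), and relevant baseline included in the model". The LOCF and WOCF sensitivity analyses in the same section use an "ANCOVA model, including the treatment group, the baseline value and the randomization strata". The TCS-dose ANCOVA in 5.7.2 also contains baseline.

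The continuous key secondary endpoints in SAP 4.4.2 are "Percent change in EASI score from baseline to week 16" and the corresponding percent change in the weekly average of daily worst itch. SAP Appendix 10.1 marks both for subgroup analysis.

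**The concern.** A programmer who follows 5.7.3 to the letter would fit baseline-adjusted ANCOVAs within each subgroup for the forest plot. The interaction p-value beside them would come from a model with no baseline term. That model is less efficient whenever baseline predicts the outcome, and interaction tests usually have low power to begin with. The covariate is already collected and already in the main model, so any loss is avoidable.

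At stake is the precision of exploratory p-values that readers will use to judge whether the effect is consistent across subgroups. No primary or key secondary conclusion depends on them.

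**Working it through.** **Text comparison.**

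| Place in SAP | Analysis | Baseline named? |
|---|---|---|
| 5.7.2 | Main ANCOVA after multiple imputation | Yes |
| 5.7.2 | LOCF and WOCF sensitivity ANCOVAs | Yes |
| 5.7.2 | TCS-dose ANCOVA | Yes |
| 5.12 | Rank-based ANCOVA for biomarker change | Yes |
| 5.7.3 | Interaction ANCOVA | No |

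The protocol's ANCOVA text (10.5.2.2) includes baseline and gives no subgroup interaction model. The plan states no power for interactions, so there is no figure of its own to reproduce.

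**Size by formula.** Let rho be the correlation between baseline and the endpoint; it is not in the documents and is varied here. Leaving baseline out multiplies the standard error (SE) of the interaction by about 1/√(1 − rho²). The last column takes an interaction that has 80% power at two-sided 0.10 with baseline in the model. Its power without baseline is Φ((1.645 + 0.842)/ratio − 1.645).

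| rho | SE ratio, without / with baseline | Power without baseline |
|---|---|---|
| 0 | 1.00 | 80% |
| 0.2 | 1.02 | 79% |
| 0.3 | 1.05 | 77% |
| 0.4 | 1.09 | 74% |
| 0.5 | 1.15 | 69% |
| 0.6 | 1.25 | 64% |

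**On the outcome scale.** Assumptions: SD 30 percentage points, a 50:50 subgroup, a 15-point interaction, and one dupilumab arm against placebo. With 110 per arm (SAP 2.2) there are 55 patients per cell.

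- SE = 30 × √(1 − rho²) × √(4/55).
- Baseline left out: SE 8.09. Baseline in the model: 8.05 at rho 0.1, 7.72 at 0.3, 7.01 at 0.5.
- Power at two-sided 0.10 = Φ(15/SE − 1.645): 58% with baseline left out; with it, 59%, 62% and 69% at those three values.

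Significance here means p below 0.10. SAP 5.7.3 prints the rule in the opposite direction, which is a separate matter.

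**Simulation check.** The interaction model of 5.7.3 was fitted with and without baseline to 330 simulated patients: three arms of 110, two binary strata factors, a binary subgroup, outcome SD 1, 500 runs per case. The table gives the mean SE of the treatment-by-subgroup term, without / with baseline. In the last column the subgroup was generated from a variable correlated 0.7 with baseline.

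| rho | Subgroup unrelated to baseline | Subgroup tied to baseline |
|---|---|---|
| 0 | 0.273 / 0.273 | 0.273 / 0.274 |
| 0.2 | 0.272 / 0.267 | 0.272 / 0.268 |
| 0.4 | 0.273 / 0.251 | 0.266 / 0.251 |
| 0.6 | 0.274 / 0.220 | 0.258 / 0.220 |

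The unrelated column agrees with the formula: 0.273/0.251 = 1.09 and 0.274/0.220 = 1.25. The ratios for a severity-linked subgroup are smaller: 0.266/0.251 = 1.06 and 0.258/0.220 = 1.17. There the subgroup term already absorbs part of the baseline effect.

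With no true interaction, rejection at the 0.10 level ran from 0.07 to 0.12 across both models. The Monte Carlo error is √(0.10 × 0.90/500) = 0.013, and neither model showed a systematic departure from 0.10.

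**The case against.** The strongest reply is that 5.7.3 never drops baseline. It refers to the ANCOVA model with the definite article, just after tying the subgroup method to 5.7.2, whose ANCOVA contains baseline. The list is limited to factors and every item in it is categorical; a model with no covariate would not be an ANCOVA. SAP 5.12 likewise keeps the two kinds of term apart: "rank-based ANCOVA model with treatment group as a fixed effect, and the relevant baseline values as covariate". Because one list serves the logistic model too, an endpoint-specific baseline may simply not have been repeated. This stands as a possible reading. Against it, every ANCOVA in the table above except the one in 5.7.3 names baseline, and the sentence needs the same clarification on either reading.

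A second reply is that the gain may be slight. Both endpoints are percent changes, already scaled by baseline, so rho could be small, and at rho 0 nothing is lost. This also stands, and it is why the size is given only as a range.

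A reader might infer that subgroups defined by baseline EASI, BSA, SCORAD or itch suffer most, since baseline differs most between their levels. The simulation does not support that: at rho 0.4 and above, such subgroups lose less than unrelated ones.

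A reader might also infer that adding baseline would bring the interaction test and the forest-plot estimates into one model. It would not. The interaction model pools the subgroups and carries a treatment-by-strata term that 5.7.2 lacks. For binary endpoints, logistic regression would still stand beside CMH.

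**Conclusion.** The point holds as a gap in specification with a modest, conditional cost. SAP 5.7.3 does not name the baseline value in the interaction model, and read literally the tests for percent change in EASI and in worst itch are not baseline-adjusted. The documents do not support the stronger statements that baseline is definitely dropped or that the p-values are necessarily less precise.

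If baseline is left out, the SE of the interaction is larger by about 0 to 5% for rho up to 0.3 and about 15% at rho 0.5, and by less for severity-defined subgroups. These figures rest on an assumed rho, and the simulation on a normal outcome with balanced arms. Type I error is not affected. The tests lie outside the hierarchy in SAP 5.7.2, so this is a minor improvement that does not touch the main conclusions.

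**What to change.** In SAP 5.7.3, extend the term list for the ANCOVA interaction model with: *and, for continuous endpoints, the relevant baseline value as a covariate*. This is one clause, it needs no new data, and it is right whether or not baseline was always intended.

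The same sentence should say which data the interaction test uses, because 5.7.3 is silent on this. Reusing the 40 imputed datasets with Rubin's formula is natural but not free of cost. The imputation model in 5.7.2 contains treatment, baseline, strata and the visit values, but no treatment-by-subgroup term, so imputed data may pull interactions toward zero. If the imputed datasets are used, the SAP should state that limitation. It should also give a pooling rule for tests with more than one degree of freedom, such as race with four levels or BSA with three.
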